### 1.5 Lobar and Superselective TACE

The lobar conventional TACE approach consists of the administration of chemotherapy and Lipiodol to via the left or right hepatic lobar branch followed by embolization. As a consequence of this approach, a large region of the liver is treated which would make it suitable for cases where there are multiple lesions within a lobe. However, this technique was also correlated to a high serum concentration of the chemotherapeutic drug after administration, which compared unfavorably to an alternate form of treatment, the drug-eluting bead TACE (DEBTACE).

While the lobar technique is still very much in use today, TACE protocols have been refined and new specialized protocols developed. The superselective approach would advance the microcatheter further into the hepatic arterial branch afferent to the segment in which the tumor is located, or if possible the tip of the catheter will be further advanced into the subsegmental branches feeding the tumor, where chemotherapy will be administered followed by embolization. In this manner, the chemotherapy is delivered in a more selective fashion, sparing more of the healthy liver parenchyma.

Logistically, the superselective approach introduces new complexities including a lengthier operation and being more technically demanding, but some studies have observed that the superselective approach may result a higher rate of complete tumor necrosis with small HCCs in comparison to the lobar approach (27-29). In Golfieri's study, tumor necrosis was greater in the superselective arm vs the lobar arm (75.1% vs 52.8%), and complete tumor necrosis was observed in approximately two times more patients on the selective arm when compared to the lobar nonselective arm, which also resulted in a reduced need for further treatments (27). The damage to liver parenchyma and function was also reduced with the superselective approach, with less adverse events when compared to the nonselective TACE (28). A superselective or subsegmental approach could also be performed in patients who may be contraindicated for conventional nonselective TACE due to severe cirrhosis and risk of serious ischemic complications (30, 31). Given the reduced adverse event profile of the subsegmental approach and the selective nature of treatment, it is conjectured that the serum doxorubicin concentration would also be decreased.

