## 5. Study Design/Investigational Plan

### 5.1 Overall Design

The study is a single site, prospective study, designed to measure the PK of doxorubicin and its metabolite doxorubicinol at various timed intervals after cTACE in patients with primary or metastatic liver cancer.

Up to 30 patients will be enrolled that meet study entry criteria; approximately 15 with primary liver cancer and 15 with secondary liver cancer. Up to 40 patients may be consented if necessary in order to enroll these 30 patients, to account for potential patients who screen-out or who are unable to complete sample collection for the PK (80% of planned draws). 15 patients will be enrolled into the lobar cTACE arm and 15 patients will be enrolled into the superselective cTACE arm. The assignment of the treatment arm will be determined by the PI or a designated radiologist after review of the patient's imaging and history.

The study is planned to complete enrollment in two years, with another month to conclude patient follow-up.

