## 7. Statistical Methods

### 7.1 Primary Outcome Variable

Pharmacokinetic profile of doxorubicin and doxorubicinol after cTACE for each patient:

- Parameters of PK analysis including peak of the plasma concentration ( $C_{max}$ ), time of maximum concentration, and area under the concentration time-curve (AUC).
- PK profiles for each patient will be correlated with toxicity and tumor burden (size of target lesion), BSA and gender.
- Comparison of PK profile between lobar administration and superselective administration.

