### 7.2 Secondary Outcome Variables

Feasibility:

- Technical success of the cTACE procedure (technical failure is defined as the inability to administer the cTACE material, in which case the patient would be excluded from the study)
- Dose of doxorubicin delivered

Safety:

- All toxicities assessed as being at least possibly related, up to the 3-4 week follow-up visit (post cTACE) will be collected. Toxicities will be analyzed by descriptive statistics to show type, grade (NCI Common Toxicity Criteria v4.0), frequency and time from cTACE.

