### 7.3 Statistical Plan

Up to 40 patients may be consented in order to enroll 30 patients, and to account for patients who are unable to complete sample collection for the PK (80% of planned draws). 15 patients will be enrolled into the lobar cTACE arm and 15 patients will be enrolled into the superselective cTACE arm.

We have assumed a clinically significant change in doxorubicin exposure would be 50%. In order to have 80% power to detect a 50% change with a 5%  $\alpha$ , the sample size varies depending on the variability noted with TACE therapy. In the Varella trial utilizing cTACE with a Lipiodol doxorubicin formulation, the variability was reported as 30% Coefficient of Variation (CV). In our recent trial (J1306) utilizing TACE with a Drug Eluting Bead (DEB) doxorubicin formulation, the variability was reported as 90% CV. We anticipate the Lipiodol formulation to behave more like the Varella trial with 15 patients allowing for slightly higher variability.

*%CV	30%	43%	90%
Expected Sample Size	8	15	58

\*Methodology/calculator accessed from the websites below on 11/6/2014:

[https://www.statstodo.com/SSizBioequiv\\_Tab.php](https://www.statstodo.com/SSizBioequiv_Tab.php)

[https://www.statstodo.com/SSizBioequiv\\_Pgm.php#](https://www.statstodo.com/SSizBioequiv_Pgm.php#)

Continuous variables will be reported as means and standard deviations, medians and ranges, or both. Categorical variables will be reported as numbers and percentages. Pharmacokinetic parameters will be calculated by standard noncompartmental methods using Phoenix WinNonlin 6.1 (Pharsight, Mountain View, CA) for each patient. Pharmacokinetic parameters will be summarized using descriptive statistics.

Comparisons of the pharmacokinetic profiles between the lobar cTACE group and the superselective cTACE group will be performed using the Mann-Whitney U test. Correlations between pharmacokinetic profiles and clinical toxicities will be performed using the Kruskal-Wallis one-way ANOVA test. Correlations between the pharmacokinetic profiles and tumor burden will be performed with the Spearman's correlation coefficient. A P value < 0.05 will be considered statistically significant in all cases.

HIC #: 1506016008  
[name]

Interim analysis:

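### The Kruskal-Wallis test of PK against toxicity in 7.3 pools two clinician-chosen arms, so a significant result could reflect arm rather than doxorubicin exposure; an arm-stratified result should stand beside it

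*Combined protocol and SAP*

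**What the plan says.** Section 7.3 gives this analysis one sentence: "Correlations between pharmacokinetic profiles and clinical toxicities will be performed using the Kruskal-Wallis one-way ANOVA test". It names no stratification, covariate or toxicity grouping. The same section adds: "A P value < 0.05 will be considered statistically significant in all cases".

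Section 7.1 lists the analysis under the primary outcome variable: "PK profiles for each patient will be correlated with toxicity and tumor burden (size of target lesion), BSA and gender". The synopsis says the study is not driven by a hypothesis, but nothing labels this particular analysis exploratory.

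On how patients reach an arm, section 5.1 says: "The assignment of the treatment arm will be determined by the PI or a designated radiologist", after a look at imaging and history. Section 1.5 describes superselective treatment as coming "with less adverse events when compared to the nonselective TACE", and of drug levels says "it is conjectured that the serum doxorubicin concentration would also be decreased". Section 1.6 describes post-embolization syndrome as common and as not depending on whether a chemotherapy drug is used. Section 5.1.1 says the amount of material given is adjusted to the area treated.

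Section 7.2 lists what will be described about toxicity: "type, grade (NCI Common Toxicity Criteria v4.0), frequency and time from cTACE". It does not say which of these forms the groups for the test.

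**The concern.** By the protocol's own account, arm may move both sides of the association. It may lower serum doxorubicin, and it may lower toxicity by routes other than doxorubicin, such as less embolized liver or a different kind of patient. If both happen, patients with high exposure and patients with more toxicity will tend to be the same lobar patients, even when exposure has no bearing on toxicity within either arm. A pooled rank test cannot tell this apart from an exposure effect.

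What is at stake is interpretation. A significant pooled result, listed under the primary outcome and judged at 0.05, could be reported as evidence that doxorubicin exposure drives toxicity when it reflects who received which technique.

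**Working it through.** **1. The plan's own figure.** Section 7.3 gives 8, 15 and 58 patients at CVs of 30%, 43% and 90%. The cited calculator is a bioequivalence page, so I used n per arm = 2 × [CV × (t₀.₉₅ + t₀.₉₀) / 0.5]², with t on 2n − 2 df. At CV 43% and n = 14 (26 df): 2 × [0.43 × (1.706 + 1.315) / 0.5]² = 13.5, so 14. The three results are 8, 14 and 57, close to the plan's. These figures size the comparison between arms. No figure is given for the PK-toxicity test.

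**2. Inputs.**
- From the documents: 30 patients, 15 per arm (8-20 allowed in 5.2); the CVs above; and the effect size, "We have assumed a clinically significant change in doxorubicin exposure would be 50" percent. A 50% change is an exposure ratio of 1.5 if read as an increase. It is a ratio of 2 if read as a halving, which is the direction conjectured in 1.5.
- Assumed: log-normal exposure; a latent toxicity score shifted between arms by 0.25, 0.5 or 1.0 SD; no exposure-toxicity link within arm; toxicity cut into two groups (60/40%), three (40/40/20%) or four (30/40/20/10%).

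**3. What arm alone can induce.** The log-scale SD is √ln(1 + CV²): 0.412 at CV 43% and 0.770 at CV 90%. The arm difference in exposure, in SD units, is dx = ln(ratio)/SD:
- CV 43%: 0.405/0.412 = 0.98 (ratio 1.5) and 0.693/0.412 = 1.68 (ratio 2)
- CV 90%: 0.53 and 0.90

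With equal arms and a toxicity shift dt, the induced pooled correlation is r = (dx·dt/4) / √[(1 + dx²/4)(1 + dt²/4)]. At CV 43%:
- ratio 1.5, dt = 1: 0.245 / √(1.240 × 1.25) = 0.20
- ratio 2, dt = 1: 0.42 / √(1.706 × 1.25) = 0.29
- ratio 2, dt = 0.25: 0.105 / √(1.706 × 1.016) = 0.08

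With 30 patients a correlation needs to be about 2.048/√(28 + 2.048²) = 0.36 to reach P < 0.05. Arm alone therefore induces something between negligible and most of the way there.

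**4. Rejection rates.** Simulation, 20,000 runs per cell for shifts of 0.5 and 1.0 SD. Pooled Kruskal-Wallis at nominal 5%, two/three/four groups:

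| CV | Ratio | 0.25 SD | 0.5 SD | 1.0 SD |
|---|---|---|---|---|
| 43% | 1.5 | 4-6% | 7/6/5% | 14/12/9% |
| 43% | 2 | 4-6% | 10/9/7% | 28/23/17% |
| 90% | 1.5 | 4-6% | 6/5/4% | 8/7/5% |
| 90% | 2 | 4-6% | 7/6/5% | 13/10/9% |

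Repeat runs agreed within about 2 points; the highest value seen at CV 43% and ratio 1.5 was 15%. With 10:20 or 20:10 arms at CV 43% the ranges for 0.5-1.0 SD are 5-13% (ratio 1.5) and 6-24% (ratio 2). If arm affects only exposure or only toxicity, the pooled test rejects in 4-5%. A rank test stratified by arm (within-arm rank covariance with permutation variance) stays at 4-5% throughout.

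A cross-check with directly assumed shares of 20/40/40% (lobar) and 60/30/10% (superselective), a shift of about 1 SD, with exposure halved and CV 43%, gave 26% pooled and 4% stratified.

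**5. Order of the grades, only if grades are used.** With no arm difference and a latent correlation of 0.3/0.5/0.6, the power of Kruskal-Wallis against Spearman is 20/56/78% against 28/69/87% with three grades, and 16/50/73% against 30/73/89% with four. The gain is 8-23 points. With two groups it is about 1 point.

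**The case against.** The strongest reply is that a pooled association is a legitimate target. Sections 7.1 and 7.3 promise correlations, not effects separate from arm, and in the scenarios above a marginal association does exist. That stands: the rejections in the table are errors only if they are read as an exposure effect.

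Second, if arm acts on toxicity only through exposure, stratifying removes real signal. That also stands, and is why the stratified result should sit beside the pooled one and not serve as a sole gate.

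Third, the links to arm are soft. The serum link is a conjecture, and the adverse-event link comes from cited studies. Section 1.5 also says the superselective approach can be used where severe cirrhosis rules out nonselective treatment, so selection could offset a lower toxicity rate. The honest lower end is no inflation. The comparison of PK between arms in 7.3 would also show part of the problem, though not the toxicity side.

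Three stronger readings are tempting. A reader might take the 60% to 80% range for post-embolization syndrome in 1.6 as a contrast between arms. It is a range for TACE patients in general and gives no rate by arm. A reader might treat the unnamed toxicity variable as the fault itself. It is a missing detail worth filling, but the confounding arises whichever variable is used. A reader might conclude that Kruskal-Wallis is the wrong test. With two groups or unordered categories it is adequate.

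**Conclusion.** The concern holds in a limited form. The plan pools two clinician-chosen arms in a test whose two sides the protocol itself links, firmly or by conjecture, to arm, and it offers nothing that would show whether a significant result is more than an arm difference.

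The size cannot be fixed from the documents. It runs from nil (small toxicity shift, or only one of the two links present) to roughly one trial in four (two groups, 1 SD shift, halved exposure, CV 43%). At the plan's preferred CV and a 1.5-fold difference it is modest. These figures rest on the assumed shifts, grade mixes and log-normal exposure, and on there being no link within arm.

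The documents do not support saying that the pooled test is invalid, that its error rate is known to be badly inflated, or that stratifying by arm would isolate an exposure effect. If treated area correlates 0.3 with both exposure and toxicity within arm, the stratified test still rejects in 6-7%; at 0.5 it rejects in 16-21%. The change is worth making because it costs little and limits what can be wrongly concluded.

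**What to change.** Add to 7.3, in words such as these: *The association between PK parameters and toxicity will be reported pooled and stratified by arm (within-arm rank test). It is exploratory. A pooled association will not be described as an exposure effect separate from arm unless the within-arm result is consistent with it in direction and size. Treated area, to which the amount administered is adjusted, may still confound the stratified result. If toxicity is analyzed as CTCAE grade with three or more occupied levels, an ordered rank test (Spearman or Jonckheere-Terpstra) will replace Kruskal-Wallis, always with its stratified version.* As a supporting detail, name the per-patient toxicity variable before PK and toxicity data are joined.

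The cost is a few sentences and standard software, with no new data. The downsides are:
- **Lower power when exposure carries the arm effect.** With overall latent correlation 0.5, ratio 2 and CV 30-43%, the stratified test has 27-35% power (two groups), 34-44% (three) or 36-47% (four), against 59-61%, 58-60% and 52-53% for pooled Kruskal-Wallis.
- **An unstratified ordered test is more exposed to arm.** With four grades, a 1 SD shift and CV 43%, Spearman rejects in 18% against 9% for Kruskal-Wallis at ratio 1.5, and 35% against 17% at ratio 2. It should not stand alone.
- **An ordered test is less sensitive to a non-monotone relation.**

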### 5.1.1 Routine Care Procedures

Patients will undergo cTACE according to the standard of care hospital protocol. Depending on the assigned treatment arm, a lobar or superselective cTACE procedure will be performed.

To perform the superselective TACE technique, the tumor-feeding arteries will be catheterized with a coaxial microcatheter passed through a 5-Fr catheter previously placed either the right or left hepatic artery. The tip of the microcatheter will be placed into the hepatic arterial branch afferent to the segment in which the tumor is located, or if possible the tip of the catheter will be further advanced into the subsegmental branches feeding the tumor. After the microcatheter placement, the chemotherapy mixture will be injected under fluoroscopy, followed by injection of 1% lidocaine and 100-300 micron embospheres.

Nonselective lobar TACE will consist of injection of the same chemotherapy materials used in the superselective procedures into the right or left lobar branches.

The amount of chemoembolization material administered is titrated to the area being treated, i.e., a smaller area (lesion) may be adequately treated with a portion of the prepared chemoembolization material. The chemoembolization material consists of 10cc of chemotherapy, with 50 mg doxorubicin and 10 mg of mitomycin-C mixed 1:1 with Lipiodol (approximately 10cc) giving a total of approximately 20cc. After the chemotherapy is administered, approximately 10cc of 1% lidocaine and 1-2 vials of embospheres measuring 100-300 microns are injected. The amount of 1% lidocaine and embospheres is titrated to each clinical situation.

Intra-arterial chemotherapy materials:

- 10 cc of chemotherapy, with 50 mg doxorubicin and 10 mg of mitomycin-C mixed 1:1 with Lipiodol (approximately 10cc) giving a total of approximately 20 cc.
- 10 cc of 1% lidocaine
- 1-2 vials of embospheres measuring 100-300 microns to achieve angiographic end-point of 2-5 heart beats to clear the contrast column.

Following the chemoembolization procedure, the patient is admitted for observation, pain control, and hydration, and is discharged home once they are stable. The day after the TACE procedure, a non-contrast CT scan is performed to document the deposition of the Lipiodol.

Follow-up imaging, labs, and clinical assessment are done 3-4 weeks following the cTACE procedure.

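### Doxorubicin dose is titrated to the treated area, so the raw correlation of AUC and Cmax with target-lesion size mixes tumor burden with dose and could be spurious or masked

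*Combined protocol and SAP*

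**What the plan says.** Section 7.1 puts the correlation under the primary outcome: "PK profiles for each patient will be correlated with toxicity and tumor burden (size of target lesion), BSA and gender". The PK measures listed there are Cmax, time of maximum concentration and AUC. Section 7.3 adds "Pharmacokinetic parameters will be calculated by standard noncompartmental methods using Phoenix WinNonlin 6.1" and, for tumor burden, "Correlations between the pharmacokinetic profiles and tumor burden will be performed with the Spearman's correlation coefficient". P < 0.05 counts as significant in every analysis.

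Section 5.1.1 describes the dosing: "The amount of chemoembolization material administered is titrated to the area being treated, i.e., a smaller area (lesion) may be adequately treated with a portion". In other words, not all of the mixture need be given. The full preparation is made up "with 50 mg doxorubicin and 10 mg of mitomycin-C mixed 1:1 with Lipiodol".

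Section 7.2 lists "Dose of doxorubicin delivered" as a feasibility outcome. No section links it to a PK analysis. Division by dose, partial correlation and stratification by arm are not mentioned for this correlation.

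**The concern.** AUC and Cmax depend on how much drug was given. If smaller lesions tend to receive fewer milligrams, lesion size can be associated with AUC through dose alone, even when tumor burden has no bearing on how much drug escapes to plasma per mg. The opposite error is also possible. If larger tumors retain more drug per mg, the larger dose given to them works against that effect and can hide it.

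At stake is how a listed element of the primary outcome is read. A significant raw correlation could be reported as an effect of tumor burden when it reflects the amount injected, or a real effect could be reported as absent. The argument applies to AUC and Cmax. It does not apply directly to time of maximum concentration.

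**Working it through.** **1. The plan's own figure.** The only sample-size figure in 7.3 is 8 / 15 / 58 patients at 30% / 43% / 90% CV for a 50% change in exposure. A two-group equivalence formula, n = 2 × [CV × (t(0.95) + t(0.90)) / 0.5]² with 2n − 2 degrees of freedom, comes close. At 43% CV it gives 2 × [0.43 × (1.708 + 1.316) / 0.5]² = 13.5, rounded up to 14. The three values are 8 / 14 / 57. The table sizes an exposure comparison; the documents give no figure for the tumor-burden correlation.

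**2. Inputs.**
- From the documents: 30 patients, 15 per arm; at most 50 mg from one preparation; CV of 30%, 43% and 90%; P < 0.05.
- Assumed, because the documents are silent: the lowest delivered dose L (40, 25 or 12.5 mg), an even spread of doses from L to 50 mg, the size-dose correlation r (0.6 on the normal scale), AUC proportional to dose, and two-sided tests.

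**3. Model with no true effect of size.** Lesion size z and noise e are standard normal. Dose = L + (50 − L) × Φ(r·z + √(1 − r²)·e). AUC = dose × lognormal error with the stated CV. With 30 patients, Spearman's rho is significant when |rho| exceeds 2.048 / √(28 + 2.048²) = 0.361.

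The CV of dose is (50 − L)/√12 divided by (50 + L)/2. For L = 12.5 this is 10.8 / 31.25 = 35%; for L = 25, 7.2 / 37.5 = 19%; for L = 40, 2.9 / 45 = 6%.

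**4. One dosing rule for all 30 patients.** Share of trials with P < 0.05 on raw AUC:

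| Doses (mg) | CV 30% | CV 43% | CV 90% |
|---|---|---|---|
| 40-50 | 10% | 8% | 6% |
| 25-50 | 42% | 26% | 11% |
| 12.5-50 | 72% | 58% | 26% |

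Repeat runs moved these by about 2 percentage points at most. Varying r from 0.4 to 0.8 over the two wider dose ranges and all three CVs gives 8% to 96%.

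**5. Lobar doses constant at 50 mg; only superselective doses follow lesion size** (43% CV, r = 0.6).
- Equal lesion sizes in the arms: about 10% (L = 25) to 14% (L = 12.5).
- Lobar target lesions 1 SD larger: 26% and 53%.
- Lobar target lesions 1 SD smaller: mean rho about −0.05, and the rate about 6%.

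So the sign can change.

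**6. Masking.** Let AUC per mg truly fall by 1 − exp(−0.2) = 18% per SD of lesion size (43% CV, 12.5-50 mg, one rule for all). The raw test detects this in about 5% of trials, the per-mg test in about 64%, and the partial Spearman correlation given dose in about 41%.

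**7. Check of the remedies.** With no true effect and one rule for all, dividing by mg returns 4-6%. That is partly by construction, since the model makes AUC proportional to dose. If instead AUC follows dose to the power 0.5 (12.5-50 mg), the per-mg test gives about 24% false positives, now with a negative correlation; partial Spearman stays near 5%. When lobar doses are constant, dose and size do not follow one common ranking across the pooled arms. The pooled partial correlation then removes the dose effect only in part, which is one reason to report by arm.

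**The case against.** A reader might infer that the dosing rule builds in a positive association, so that the tumor-burden result would be spurious. The documents do not support that.

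- Section 5.1.1 says only that a smaller lesion may need a portion of the mixture. It gives no minimum, no spread and no frequency of partial dosing. If nearly everyone receives 40-50 mg, the distortion is small.
- Half the planned patients are in the lobar arm. Section 1.5 describes lobar treatment as covering a large region and suiting several lesions in one lobe, so treated area there need not follow target-lesion size. Step 5 shows that pooling can weaken, cancel or slightly reverse the association.
- The magnitudes rest on assumed inputs. Doses spread evenly over 12.5-50 mg already have a 35% CV, more than the 30% that 7.3 takes from the cited cTACE trial. If that 30% describes raw exposure, the 72% cell is not coherent.
- Raw AUC and Cmax are the patient's actual systemic exposure, which the synopsis says is of interest. A raw correlation with lesion size is a valid description of exposure under routine dosing. It misleads only if read as an effect of burden apart from dose, and the plan does not state that reading.
- The synopsis says the study is not hypothesis driven, no decision hangs on this correlation, and delivered dose could be used later.

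All of this stands as a limit on strength. It does not remove the point: the plan ties dose to treated area, correlates exposure with lesion size, attaches a significance threshold, and does not say how dose enters. The lack of any stated dose spread is a reason to settle the analysis before the data are seen.

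**Conclusion.** The point holds in a conditional form. The planned raw Spearman correlation of AUC and Cmax with target-lesion size cannot separate tumor burden from dose, so the result could be spurious or masked. Neither the size nor the sign of the distortion can be found from the documents. At 43% CV and r = 0.6, the chance of P < 0.05 with no true effect runs from about 8% to 58% under one dosing rule, depending on the dose range. It is about 10-14% with constant lobar doses and equal lesion sizes. All of these rest on the assumed dose range, size-dose link and dose proportionality. The raw result is not wrong; it answers a question about total exposure and should be labelled so.

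**What to change.** In 7.3, for AUC and Cmax only (not time of maximum concentration), report the tumor-burden Spearman correlation in three forms, overall and by arm:
- raw, labelled as total exposure under area-titrated dosing;
- partial Spearman given mg of doxorubicin delivered;
- Spearman on the parameter divided by mg delivered.

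State that any claim about an effect of tumor burden apart from dose will rest on the two dose-accounted forms. If dose turns out not to vary within an arm, the partial correlation is undefined there and the raw and per-mg forms coincide.

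The cost is a few lines of text and no new data, since delivered dose is already a secondary outcome. There are three drawbacks. Dividing by mg assumes rough dose proportionality. The partial correlation does not, but it loses power (about 41% against 64% in the masking case). By-arm results are descriptive, since with 15 patients |rho| must exceed 2.160 / √(13 + 2.160²) = 0.514 to reach P < 0.05. No change to dosing is proposed.
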